## 6.9. Previous and Concomitant Therapy

For 24-week and 52-week interim analyses, summaries of previous and concomitant medications will be based on the ITT population.

Summaries of previous and concomitant medications will be based on the ITT population.

At screening, previous and current AD treatments are recorded for each patient. Concomitant therapy for the treatment period is defined as therapy that starts before or during the treatment period and ends during the treatment period or is ongoing (has no end date or ends after the treatment period). Should there be insufficient data to make this comparison (for example, the concomitant therapy stop year is the same as the treatment start year, but the concomitant therapy stop month and day are missing), the medication will be considered concomitant for the treatment period.

Summaries of previous medications will be as follows:

- Previous AD therapies

Summaries of concomitant medications, with sponsor and non-sponsor provided background TCS included, will be as follows:

- General concomitant medications excluding rescue medicine

## 6.10. Efficacy Analyses

The general methods used to summarize efficacy data, including the definition of baseline value for assessments are described in Section 6.2.2.

Efficacy analyses will generally be analyzed according to the following formats and patients will be analyzed according to the investigational product to which they were randomized at Week 0 (Visit 2):

- Week 0 to Week 24 with data up to rescue (primary censoring rule)
- Week 0 to Week 24, including data after rescue to nonsystemic therapy for primary and key secondary objectives (secondary censoring rule)
- Week 0 to Week 52, including data after rescue to nonsystemic therapy for objectives evaluated at Week 52 (secondary censoring rule)
- Week 0 to Week 52, including data after rescue to nonsystemic therapy for IGA01, IGA012, EASI75, EASI $\leq$ 7, Itch 4-point improvement, SCORAD $\leq$ 25, DLQI total score $\leq$ 5 at Week 52 (primary censoring rule)

For the Long-Term Extension Period 3 and Bridging Extension Period 4, efficacy endpoints specified in Section 4.2.2 and Section 4.3 will be summarized with below situations:

- Patients entered the Substudy, descriptive statistics for Week 52 through Week 104, Week 104 through Week 200 will be presented in Week 104 DBL and Final DBL, respectively. The summaries will include data up to respective DBL subject to LTE Substudy censoring rule.

- Patients entered the Substudy and relapsed, Time to event analyses such as summary of Time to Retreatment, and the Kaplan-Meier plot of Time to Relapse will be provided.
- For the LTE Non-responders population, descriptive statistics for Week 52 through Week 104, Week 104 through Week 200 will be presented in Week-104 DBL and Final DBL, respectively. The summaries will include data up to respective DBL subject to LTE Non-responder censoring rule.

[Table JAIN.6.7](#) includes the descriptions and derivations of the primary, secondary, and exploratory efficacy outcomes (IGA, EASI, BSA, SCORAD).

[Table JAIN.6.8](#) and [Table JAIN.6.9](#) provides the detailed analyses including analysis type, method and imputation, population, time point, and comparisons for efficacy analyses.

Descriptions, derivations and analyses of Health Outcomes/Quality-of-Life Measures (for example, NRS, ADSS, POEM) are detailed in Section [6.11](#).

Table JAIN.6.7. Description and Derivation of Primary, Secondary, and Exploratory Efficacy Outcomes

Measure	Description	Variable	Derivation / Comment	Imputation Approach if with Missing Components
Eczema Area and Severity Index (EASI)	The EASI assesses objective physician estimates of 2 dimensions of atopic dermatitis – disease extent and clinical signs (Hanifin et al. 2001) – by scoring the extent of disease (percentage of skin affected: 0 = 0%; 1 = 1-9%; 2 = 10-29%; 3 = 30-49%; 4 = 50-69%; 5 = 70-89%; 6 = 90-100%) and the severity of 4 clinical signs (erythema, edema/papulation, excoriation, and lichenification) each on a scale of 0 to 3 (0 = none, absent; 1 = mild; 2 = moderate; 3 = severe) at 4 body sites (head and neck, trunk, upper limbs, and lower limbs). Half scores are allowed. Each body site will have a score that ranges from 0 to 72, and the final EASI score will be obtained by weight-averaging these 4 scores. Hence, the final EASI score will range from 0 to 72 for each time point.	
 
EASI score
 
	
Derive EASI region score for each of head and neck, trunk, upper limbs, and lower limbs as follows:
 $\text{EASI}_{\text{region}} = (\text{Erythema} + \text{edema/papulation} + \text{Excoriation} + \text{Lichenification}) * (\text{value from percentage involvement})$ 
where erythema, edema/papulation, excoriation, and lichenification are evaluated on a scale of 0 to 3 and value from percentage involvement is on a scale of 0 to 6.
 
Then total EASI score is as follows:
 $\text{EASI} = 0.1 * \text{EASI}_{\text{head and neck}} + 0.3 * \text{EASI}_{\text{trunk}} + 0.2 * \text{EASI}_{\text{upper limbs}} + 0.4 * \text{EASI}_{\text{lower limbs}}$	N/A – partial assessments cannot be saved.
		
 
Change from baseline in EASI score
 
	
Change from baseline: observed EASI score – baseline EASI score
 
% change from baseline:
 $100 \times \frac{\text{Observed score} - \text{Baseline}}{\text{Baseline}}$	Missing if baseline or observed value is missing.
		
 
Percent change from baseline EASI score
 
		
		
 
EASI50
 
	
% Improvement in EASI score from baseline <math>\geq 50\%</math>:
 
% change from baseline <math>\leq 50</math>
	Missing if baseline or observed value is missing.
		
 
EASI75
 
	
% Improvement in EASI score from baseline <math>\geq 75\%</math>:
 
% change from baseline <math>\leq 75</math>
	Missing if baseline or observed value is missing.
		
 
EASI90
 
	
% Improvement in EASI score from baseline <math>\geq 90\%</math>:
 
% change from baseline <math>\leq 90</math>
	Missing if baseline or observed value is missing.

Measure	Description	Variable	Derivation / Comment	Imputation Approach if with Missing Components
		
 
• Time to reaching EASI75
 
	First time reaching EASI75 as event 1, rescue and discontinue for lack of efficacy as event 2, censor up to Week 16	Use observed value, rescue and discontinue for lack of efficacy as competing event, censor up to Week 16.
		
 
• Absolute EASI≤7
 
	Total EASI score≤7	N/A – partial assessments cannot be saved.
Validated Investigator's Global Assessment for AD (vIGA AD)	The validated Investigator's global assessment of the patient's overall severity of their AD, based on a static, numeric 5-point scale from 0 (clear) to 4 (severe). The score is based on an overall assessment of the degree of erythema, papulation/induration, oozing/crusting, and lichenification.	
 
• IGA score
 
• Change from baseline in IGA score
 
• IGA (0,1) with <math>\geq 2</math>-point improvement
 
• IGA (0)
 
	
Single item. Range: 0 to 4 0 represents “clear” 4 represents “severe”
 
Change from baseline: observed IGA score – baseline IGA score
 
 
• Observed score of 0 or 1 and change from baseline <math>\leq -2</math>
 
• Observed score of 0
 
	
Single item, missing if missing.
 
Missing if baseline or observed value is missing.
 
 
• Missing if baseline or observed value is missing.
 
• Single item, missing if missing.
 

		
 
• Time to reaching first IGA (0,1)
 
	First time reaching IGA (0,1) as event 1, rescue and discontinue for lack of efficacy as event 2, censor up to Week 16	Use observed value, rescue and discontinue for lack of efficacy as competing event, censor up to Week 16.

Measure	Description	Variable	Derivation / Comment	Imputation Approach if with Missing Components
Body Surface Area (BSA) Affected by AD	
Body surface area affected by AD will be assessed for 4 separate body regions and is collected as part of the EASI assessment: head and neck, trunk (including genital region), upper extremities, and lower extremities (including the buttocks). Each body region will be assessed for disease extent ranging from 0% to 100% involvement. The overall total percentage will be reported based on all 4 body regions combined, after applying specific multipliers to the different body regions to account for the percent of the total BSA represented by each of the 4 regions.
	
 
BSA score
 
	
Use the percentage of skin affected for each region (0% to 100%) in EASI as follows:
 $\text{BSA} = \text{BSA}_{\text{head and neck}}/100/0.10 + \text{BSA}_{\text{trunk}}/100/0.0333 + \text{BSA}_{\text{upper limbs}}/100/0.05 + \text{BSA}_{\text{lower limbs}}/100/0.025$	N/A – partial assessments cannot be saved.
			
 
Change from baseline in BSA score
 
	Missing if baseline or observed value is missing.
Scoring Atopic Dermatitis (SCORAD)	
The Scoring Atopic Dermatitis index uses the rule of nines to assess disease extent (head and neck 9%; upper limbs 9% each; lower limbs 18% each; anterior trunk 18%; back 18%; and genitals 1%). It evaluates 6 clinical characteristics to determine disease severity: (1) erythema, (2) edema/papulation, (3) oozing/crusts, (4) excoriation, (5) lichenification, and (6) dryness on a scale of 0 to 3 (0 = absence, 1 = mild, 2 = moderate, 3 = severe). The SCORAD index also assesses
	
 
SCORAD score
 
	$\text{SCORAD} = A/5 + B/2 + C$ , where A is extent of disease, range 0-100 B is disease severity, range 0-18 C is subjective symptoms, range 0-20	Missing if components A and B are missing or if component C is missing. Partial assessments performed by physician cannot be saved and partial assessments performed by subject cannot be saved.
			
 
Change from baseline in SCORAD score
 
	Missing if baseline or observed value is missing.
			
 
Percent change from baseline in SCORAD score
 
	% change from baseline: $100 \times \frac{\text{Observed score} - \text{Baseline}}{\text{Baseline}}$

Measure	Description	Variable	Derivation / Comment	Imputation Approach if with Missing Components
	subjective symptoms of pruritus and sleep loss in the last 72 hours on visual analogue scales (VAS) of 0 to 10 where 0 is no itch or sleep loss and 10 is worst imaginable itch or sleep loss. These 3 aspects: extent of disease, disease severity, and subjective symptoms combine to give a maximum possible score of 103 (Stalder et al. 1993; Kunz et al. 1997; Schram et al. 2012).	• SCORAD75	% Improvement in SCORAD from baseline $\geq 75\%$ : % change from baseline $\leq 75$	Missing if baseline or observed value is missing.
		• SCORAD90	% Improvement in SCORAD from baseline $\geq 90\%$ : % change from baseline $\leq 90$	Missing if baseline or observed value is missing.

Abbreviations: AD = atopic dermatitis; EASI50 = 50% improvement from baseline in Eczema Area and Severity Index score; EASI75 = 75% improvement from baseline in Eczema Area and Severity Index score; EASI90 = 90% improvement from baseline in Eczema Area and Severity Index score; N/A = not applicable; SCORAD75 = 75% decrease from baseline in Scoring Atopic Dermatitis values; SCORAD90 = 90% decrease from baseline in Scoring Atopic Dermatitis values.

Table JAIN.6.8. Description of Primary, Secondary, and Exploratory Efficacy Analyses (Period 2)

Measure	Variable	Analysis Method (Section 6.2.2)	Population (Section 6.2.1)	Comparison a /Time Point	Analysis Type
Eczema Area and Severity Index (EASI) [categorical]	• Proportion of patients achieving EASI75	Logistic regression using NRI (both censoring rules, respectively)	ITT	Bari 4-mg or Bari 2-mg or Bari 1-mg vs PBO; Week 16	Primary analysis (censoring rule #1)
		Logistic regression using NRI (both censoring rules, respectively)	ITT	Bari 4-mg or Bari 2-mg or Bari 1-mg vs PBO; Week 24, 52	Key secondary analysis for Week 24
		Logistic regression using NRI; with treatment-by-region interaction (censoring rule #1) b	ITT	Bari 4-mg or Bari 2-mg vs Bari 1-mg vs PBO; Week 16, 24	Sensitivity analysis
		Logistic regression using NRI (censoring rule #1)	PPS	Bari 4-mg or Bari 2-mg or Bari 1-mg vs PBO; Week 16, 24	Sensitivity analysis
		Logistic regression using pMI (censoring rule #1)	ITT	Bari 4-mg or Bari 2-mg or Bari 1-mg vs PBO; Week 16, 24	Sensitivity analysis
		Tipping point analysis (censoring rule #1)	ITT	Bari 4-mg or Bari 2-mg vs Bari 1-mg PBO; Week 16, 24	Sensitivity analysis
	• Proportion of patients achieving EASI90	Logistic regression using NRI (both censoring rules, respectively)	ITT	Bari 4-mg or Bari 2-mg or Bari 1-mg vs PBO; Week 16, 52	Key secondary analysis for Week 16
		Logistic regression using NRI (censoring rule #1)	PPS	Bari 4-mg or Bari 2-mg or Bari 1-mg vs PBO; Week 16	Sensitivity analysis
		Logistic regression using pMI (censoring rule #1)	ITT	Bari 4-mg or Bari 2-mg or Bari 1-mg vs PBO; Week 16	Sensitivity analysis
		Logistic regression using NRI (censoring rule #1)	ITT	Bari 4-mg or Bari 2-mg or Bari 1-mg vs PBO; Week 16	Exploratory analysis
	• Proportion of patients achieving EASI50	Logistic regression using NRI (censoring rule #1)	ITT	Bari 4-mg or Bari 2-mg or Bari 1-mg vs PBO; Week 16	Secondary analysis for Week 16

Measure	Variable	Analysis Method (Section 6.2.2)	Population (Section 6.2.1)	Comparison a /Time Point	Analysis Type
	• Proportion of patients achieving EASI≤7	Logistic regression using NRI (censoring rule #1)	ITT	Bari 4-mg or Bari 2-mg or Bari 1-mg vs PBO; Week 16	Exploratory analysis
Eczema Area and Severity Index (EASI) [continuous]	• EASI score percent change from baseline	MMRM (both censoring rules, respectively at Week 16 and #2 at Week 52)	ITT	Bari 4-mg or Bari 2-mg or Bari 1-mg vs PBO; Week 16, 52	Key secondary analysis for Week 16
		MMRM (censoring rule #1)	PPS	Bari 4-mg or Bari 2-mg or Bari 1-mg vs PBO; Week 16	Sensitivity analysis
		ANCOVA; mLOCF (censoring rule #1)	ITT	Bari 4-mg or Bari 2-mg or Bari 1-mg vs PBO; Week 16	Sensitivity analysis
		ANCOVA; pMI (censoring rule #1)	ITT	Bari 4-mg or Bari 2-mg or Bari 1-mg vs PBO; Week 16	Sensitivity analysis
		ANCOVA; mBOCF (censoring rule #1)	ITT	Bari 4-mg or Bari 2-mg or Bari 1-mg vs PBO; Week 16	Sensitivity analysis
		MMRM & ANCOVA; mLOCF (censoring rule #1 at Week 16 and #2 at Week 52)	ITT	Bari 4-mg or Bari 2-mg or Bari 1-mg vs PBO; Week 16, 52	Exploratory analysis
Validated Investigator's Global Assessment for AD (vIGA AD)	• EASI score change from baseline	MMRM & ANCOVA; mLOCF (censoring rule #1)	ITT	Bari 4-mg or Bari 2-mg or Bari 1-mg vs PBO; Week 16, 52	Exploratory analysis
		Logistic regression using NRI (both censoring rules, respectively)	ITT	Bari 4-mg or Bari 2-mg or Bari 1-mg vs PBO; Week 16, 24, 52	Key secondary analysis for Week 16 and 24 (censoring rule #1)
	• Proportion of patients achieving IGA (0,1) with a ≥2-point improvement	Logistic regression using NRI; with treatment-by-region interaction (censoring rule #1) b	ITT	Bari 4-mg or Bari 2-mg vs PBO; Week 16, 24	Sensitivity analysis

Measure	Variable	Analysis Method (Section 6.2.2)	Population (Section 6.2.1)	Comparison a /Time Point	Analysis Type	
		Logistic regression using NRI (censoring rule #1)	PPS	Bari 4-mg or Bari 2-mg or Bari 1-mg vs PBO; Week 16, 24	Sensitivity analysis	
		Logistic regression using pMI (censoring rule #1)	ITT	Bari 4-mg or Bari 2-mg or Bari 1-mg vs PBO; Week 16, 24	Sensitivity analysis	
		Tipping point analysis (censoring rule #1)	ITT	Bari 4-mg or BARI 2-mg vs Bari 1-mg vs PBO; Week 16, 24	Sensitivity analysis	
		• Proportion of patients achieving IGA (0,1) with a $\geq 2$ -point improvement	Logistic regression using NRI (censoring rule #1)	ITT	Bari 4-mg or Bari 2-mg or Bari 1-mg vs PBO; Week 4	Secondary analysis
		• Proportion of patients achieving IGA (0)	Logistic regression using NRI (censoring rule #1)	ITT	Bari 4-mg or Bari 2-mg or Bari 1-mg vs PBO; Week 16	Secondary analysis
Body Surface Area (BSA) Affected by AD	• BSA change from baseline	MMRM (censoring rule #1 at Week 16 and #2 at Week 52)	ITT	Bari 4-mg or Bari 2-mg or Bari 1-mg vs PBO; Week 16, 52	Secondary analysis for Week 16	
		ANCOVA; mLOCF (censoring rule #1 at Week 16 and #2 at Week 52)	ITT	Bari 4-mg or Bari 2-mg or Bari 1-mg vs PBO; Week 16, 52	Sensitivity analysis for Week 16	
Scoring Atopic Dermatitis (SCORAD) [categorical]	• Proportion of patients achieving SCORAD75	Logistic regression using NRI (both censoring rules, respectively at Week 16 and #2 at Week 52)	ITT	Bari 4-mg or Bari 2-mg or Bari 1-mg vs PBO; Week 16, 52	Key secondary analysis for Week 16	
		Logistic regression using NRI (censoring rule #1)	PPS	Bari 4-mg or Bari 2-mg or Bari 1-mg vs PBO; Week 16	Sensitivity analysis	
		Logistic regression using pMI (censoring rule #1)	ITT	Bari 4-mg or Bari 2-mg or Bari 1-mg vs PBO; Week 16	Sensitivity analysis	
	• Proportion of patients achieving SCORAD90	Logistic regression using NRI (censoring rule #1)	ITT	Bari 4-mg or Bari 2-mg or Bari 1-mg vs PBO; Week 16	Secondary analysis for Week 16	

Measure	Variable	Analysis Method (Section 6.2.2)	Population (Section 6.2.1)	Comparison a /Time Point	Analysis Type
	• Proportion of patients achieving SCORAD $\leq 25$ (in the subset of patients with SCORAD $> 25$ at baseline)	Logistic regression using NRI (censoring rule #1)	ITT	Bari 4-mg or Bari 2-mg or Bari 1-mg vs PBO; Week 16	Exploratory analysis
Scoring Atopic Dermatitis (SCORAD) [continuous]	• SCORAD score change from baseline	MMRM (censoring rule #1 at Week 16 and #2 at Week 52)	ITT	Bari 4-mg or Bari 2-mg or Bari 1-mg vs PBO; Week 16, 52	Secondary analysis for Week 16
		ANCOVA; mLOCF (censoring rule #1 at Week 16 and #2 at Week 52)	ITT	Bari 4-mg or Bari 2-mg or Bari 1-mg vs PBO; Week 16, 52	Sensitivity analysis for Week 16
	• SCORAD score percent change from baseline	MMRM & ANCOVA; mLOCF (censoring rule #1 at Week 16 and #2 at Week 52)	ITT	Bari 4-mg or Bari 2-mg or Bari 1-mg vs PBO; Week 16, 52	Exploratory analysis

Abbreviations: AD = atopic dermatitis; ANCOVA = analysis of covariance; Bari = baricitinib; EASI50 = 50% improvement from baseline in Eczema Area and Severity Index score; EASI75 = 75% improvement from baseline in Eczema Area and Severity Index score; EASI90 = 90% improvement from baseline in Eczema Area and Severity Index score; ITT = intent-to-treat; mLOCF = modified last observation carried forward; MMRM = mixed model repeated measures; NRI = nonresponder imputation; NRS = Numeric Rating Scale; PBO = placebo; pMI = placebo multiple imputation; PPS = per protocol set; TCS = TCS = topical corticosteroids.

Notes: missing data related to COVID-19 may be imputed using the method specified in Section 6.3.7.

- a The addition of the background therapy to the treatment arms (“+ TCS”) has been omitted to save space and ease the reading.
- b This analysis will only be done in case there are sufficient patient numbers per regions to allow the factor “region” in the main analysis model. See Section 6.2.2.2 for details.

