### 3. Revision History

Statistical Analysis Plan (SAP) Version 1 is based on Protocol I4V-MC-JAIN(b) and was approved prior to the first unblinding.

Statistical Analysis Plan Version 2 is based on Protocol I4V-MC-JAIN(d) and Program Statistical Analysis Plan (PSAP) Version 6. The purpose of SAP Version 2 is to describe and document the 24-week interim analysis. The analysis for assessment after Week 24, Treatment Period 3, including the down-titration substudy of JAIN will be described in a subsequent version of this SAP.

Statistical Analysis Plan Version 3 is based on Protocol I4V-MC-JAIN(e) and PSAP Version 7. The purpose of SAP Version 3 is to describe and document the 52-week interim analysis.

The changes incorporated in Version 3 are as follows:

Change	Section	Summary of Change
Exploratory Objectives	Section 4.3	Added exploratory objectives for 52-week interim analysis
Study Design	Section 5	Aligned with the protocol (e)
Analysis Population	Section 6.2.1	Updated analysis period for safety analyses for 52-week interim analysis
General Considerations for the analyses for 52-week interim analysis	Section 6.2.2	Updated diary data analyses for 52-week interim analysis
Missingness due to COVID19	Section 6.3.7	Added for missingness due to COVID19
	Table 6.7	Updated for 52-week interim analysis
	Table 6.9	Updated for 52-week interim analysis

**Statistical Analysis Plan Version 4** is based on Protocol I4V-MC-JAIN(e) and PSAP Version 7. The purpose of SAP Version 4 is to describe and document the Week-104 interim analysis, with the projected database lock (DBL) in July, 2021.

The changes incorporated in Version 4 are as follows:

Change	Section	Summary of Change
Secondary Objectives	Section 4.2.2	Added Secondary Objectives for Period 3 analyses
Exploratory Objectives	Section 4.3	Added Exploratory Objectives for Period 3 analyses
Analysis Populations	Section 6.2.1	Added analysis populations for Period 3 and Period 4 Efficacy and Safety analysis
Definition of Baseline and Postbaseline Measures	Section 6.2.2.1	Extended to study visits to Week 104; For daily dairy data, extended to Week 68; define the baseline period for Period 3 safety analyses
Handling of Dropouts or Missing Data	Section 6.3	Added the Censoring rule for Period 3 Efficacy analyses
Imputation Techniques for Various Variables	Table 6.3	Added mLOCF for Period 3 Efficacy analyses

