Missingness due to COVID-19	Section 6.3.7	Added a sentence about not implementing a special missing imputation method if the missing data due to Covid-19 does not exceed 5%.
Patient Disposition	Section 6.5	Added disposition summary for Period 3 and Period 4.
Treatment Compliance	Section 6.7	Added compliance and exposure summary for Period 3
Extent of Exposure	Section 6.13.1	
Background Therapy	Section 6.8	Added TCS summary for Period 3
Efficacy Analyses	Section 6.10	Added a paragraph for Period 3 Efficacy analyses description
Description of Efficacy analysis	Table 6.7 and Table 6.9	Modified the table to include all Efficacy measurements analyses for Week-104 DBL

Change	Section	Summary of Change
Safety Analysis Populations	Table 3.1	Added LTE populations for Period 3 Safety analyses
Safety Analyses	Section 6.13	Added the scope of safety analyses for the Week-104 interim lock

Statistical analysis plan (SAP) Version 5 was approved prior to final DBL. Baricitinib is approved for moderate-to-severe Atopic Dermatitis in over 50 countries. Based on widespread approval, Lilly have made the decision to begin closure of sites in countries where there is regulatory approval and reimbursement. This is being rolled out in a phased” approach based on country approval and accessibility. Patients have been rolled off following confirmation that baricitinib is available locally. Individual unblinding has been provided to guide transition to commercial product while blinding has been maintained for patients remaining in the trial. All unblinding occurred after Week 104 DBL. The protocol did not include any primary or secondary endpoints beyond Week 104 and there was no critical regulatory commitments or publications that would warrant preservation of the blind until the final DBL.

This version of the SAP pertains to the analysis at Final DBL. The changes incorporated in Version 5 are summarized as follows:

Change	Section	Summary of Change
Table Title	Table 6.1 and Table 6.3	Updated Title. Added Word “Analysis” in the end of Title for Table 6.1. Added word “Final DBL” in the end of the Title for Table 6.3 Upated table content for “Safety Population” of Table 6.3
General consideration for Analyses	Section 6.2.2	Added General consideration for Period 4 (beyond Week 104) analyses
Health Outcomes and Quality-of-Life Measures Analyses	Table 6.12	Updated Timepoint for endpoints Itch NRS , Skin Pain NRS, ADSS, and PGI-S AD

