- Null Hypothesis[ITCH W4]: Proportion of baricitinib 4-mg patients achieving a 4-point improvement in Itch NRS is equal to the proportion of placebo patients achieving a 4-point improvement in Itch NRS at Week 4 among patients with baseline Itch NRS score  $\geq 4$ .
- Null Hypothesis[SCORAD75]: Proportion of baricitinib 4-mg patients achieving SCORAD75 is equal to the proportion of placebo patients achieving SCORAD75 at Week 16.
- Null Hypothesis[EASI 90]: Proportion of baricitinib 4-mg patients achieving EASI90 is equal to the proportion of placebo patients achieving EASI90 at Week 16.
- Null Hypothesis[PAIN NRS]: Mean change from baseline in Skin Pain NRS for baricitinib 4-mg patients is equal to the mean change from baseline in Skin Pain NRS for placebo patients at Week 16.
- Null Hypothesis[ADSS2 W16]: Mean change from baseline in ADSS Item 2 score for baricitinib 4-mg patients is equal to the mean change from baseline in ADSS Item 2 score for placebo patients at Week 16.
- Null Hypothesis[ITCH W2]: Proportion of baricitinib 4-mg patients achieving a 4-point improvement in Itch NRS is equal to the proportion of placebo patients achieving a 4-point improvement in Itch NRS at Week 2 among patients with baseline Itch NRS score  $\geq 4$ .
- Null Hypothesis[ADSS2 W1]: Mean change from baseline ADSS Item 2 the score for baricitinib 4-mg patients is equal to the mean change from baseline in ADSS Item 2 score for placebo patients at Week 1.
- Null Hypothesis[ITCH W1]: Proportion of baricitinib 4-mg patients achieving a 4-point improvement in Itch NRS is equal to the proportion of placebo patients achieving a 4-point improvement in Itch NRS at Week 1 among patients with baseline Itch NRS score  $\geq 4$ .

*Baricitinib 2 mg:*

[figure not shown]
- Null Hypothesis[IGA01 W16]: Proportion of baricitinib 2-mg patients achieving IGA of 0 or 1 with a  $\geq 2$ -point improvement from baseline is equal to the proportion of placebo patients achieving IGA of 0 or 1 with a  $\geq 2$ -point improvement from baseline at Week 16.
- Null Hypothesis[IGA01 W24]: Proportion of baricitinib 2-mg patients achieving IGA of 0 or 1 with a  $\geq 2$ -point improvement from baseline is equal to the proportion of placebo patients achieving IGA of 0 or 1 with a  $\geq 2$ -point improvement from baseline at Week 24.
- Null Hypothesis[EASI75 W24]: Proportion of baricitinib 2-mg patients achieving EASI75 is equal to the proportion of placebo patients achieving EASI75 at Week 24.

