## 6.6. Patient Characteristics

Patient characteristics including demographics and baseline characteristics will be summarized descriptively for the **24-week interim analysis** (ITT population), and Final analysis (LTE Substudy Population and LTE Non-responder Populations, and LTE responders/partial responders who did not enter the Substudy).

Historical illnesses and pre-existing conditions will be summarized descriptively for the **24-week interim analysis** (ITT population) by treatment group for the ITT population.

No formal statistical comparisons will be made among treatment groups unless otherwise stated.

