### **6.6.2. Baseline Disease Characteristics**

The following baseline disease information will be categorized and presented for baseline AD clinical characteristics, baseline health outcome measures, and other baseline demographic and disease characteristics as described above:

- Duration since AD diagnosis (years)
- Duration since AD diagnosis category (0 to <2 years, 2 years to <5 years, 5 years to <10 years, 10 years to <20 years,  $\geq$ 20 years)
- Age at Diagnosis (years)
- Age Group at Diagnosis (<18 years,  $\geq$ 18 years to <50 years,  $\geq$ 50 years)
- Habits (Alcohol: Never, Current, Former; Tobacco: Never, Current, Former)
- Skin Infections treated with a pharmacological agent within past year (yes, no, unknown; number if yes)
- Atopic Dermatitis Flares within past year (yes, no, unknown; number if yes)
- Validated IGA score
- Eczema Area and Severity Index (EASI) score
- Scoring Atopic Dermatitis (SCORAD)
- Body Surface Area (BSA) affected by AD
- Hospital Anxiety Depression Scale (HADS) subscales
- Patient Oriented Eczema Measure (POEM)
- Itch Numeric Rating Scale (NRS)
- Atopic Dermatitis Sleep Scale (ADSS) Item 2
- Dermatology Life Quality Index (DLQI)
- Skin Pain NRS
- Patient Global Impression of Severity AD (PGI-S-AD)
- Baseline renal function status: impaired (estimated glomerular filtration rate [eGFR] <60 mL/min/1.73 m^2) or not impaired (eGFR  $\geq$ 60 mL/min/1.73 m^2)

- Immunoglobulin E (IgE): intrinsic (<200 kU/I) or extrinsic ( $\geq 200$  kU/I)
- Prior therapy
  - Topical therapy only
  - Systemic therapy only
- Prior phototherapy use
  - Yes, No
  - Yes (type of phototherapy), No
  - If yes, reason for discontinuation of latest phototherapy
- Prior topical calcineurin inhibitor (TCNI) therapy use
  - Yes, No (reason for not using TCNI)
- Prior cyclosporine use (all prior uses, independent of the outcome)
  - Yes, No
- Prior cyclosporine use (cyclosporine ineligible, eligibility criteria)
  - Yes, No

Note: Cyclosporine ineligible (yes, no)

Set to “yes” if the following reasons were selected for either not using the medication or discontinuing the medication:

- Reason for not using the medication: contraindication
- Reason for discontinuation (at least once in case patient took cyclosporine on several occasions): inadequate response, intolerance to medication, or contraindication

All patients in JAIN should be cyclosporine ineligible.

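### SAP Table JAIN.6.7: the SCORAD formula as printed reaches 49, not the stated 103; if it was programmed, SCORAD75 status could be misclassified

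*SAP*

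**What the plan says.** The SCORAD row of Table JAIN.6.7 (SAP Section 6.10) gives the derivation A/5 + B/2 + C, "where A is extent of disease, range 0-100 B is disease severity, range 0-18 C is subjective symptoms, range 0-20". The description in that row says that the three components "combine to give a maximum possible score of 103", and protocol Section 9.1.2.2 gives the same maximum. Neither document contains another SCORAD formula.

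The score feeds an alpha-controlled test. One null hypothesis in SAP Section 6.4 is "Proportion of baricitinib 4-mg patients achieving SCORAD75 is equal to the proportion of placebo patients achieving SCORAD75 at Week 16", and there are matching hypotheses for 2-mg and 1-mg. It also feeds SCORAD90 and mean SCORAD change (other secondary) and SCORAD<=25 among patients above 25 at baseline (exploratory).

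SAP Section 3 sets out which version served which database lock. For the first efficacy lock, "The purpose of SAP Version 2 is to describe and document the 24-week interim analysis". For the next, "The purpose of SAP Version 3 is to describe and document the 52-week interim analysis". The text available here is Version 5: "This version of the SAP pertains to the analysis at Final DBL".

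**The concern.** A score cannot have a maximum of 103 if its own formula and component ranges stop at 49. The printed line is also the only derivation in the documents that a programmer could follow.

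A wrong constant on the whole score would cancel in percent change and leave SCORAD75 alone. This discrepancy would not cancel, because it sits on one term only: the severity component would be weighted one seventh as heavily as 103 implies, relative to extent and symptoms. If that formula had been used, some patients could fall on the wrong side of the 75% line in a test that takes part in the graphical procedure. The absolute cut-off of 25, and the baseline subset defined by it, would be applied to a 0-49 scale.

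**Working it through.** **Inputs.** Formula, ranges and the figure 103: SAP Table JAIN.6.7, SCORAD row. Second source for 103: protocol Section 9.1.2.2.

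**1. Are the ranges right?** The row's own description confirms them.
- A: the listed body areas sum to 9 + 2×9 + 2×18 + 18 + 18 + 1 = 100.
- B: six signs scored 0 to 3 give 6×3 = 18.
- C: two scales of 0 to 10 give 2×10 = 20.

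**2. Does the formula reproduce 103?** As printed, 100/5 + 18/2 + 20 = 20 + 9 + 20 = 49. It does not.

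**3. Which single change restores 103?**
- B term: (103 − 20 − 20)/18 = 3.5, that is 7B/2. Check: 20 + 63 + 20 = 103.
- A term: (103 − 9 − 20)/100 = 0.74.
- C term: (103 − 20 − 9)/20 = 3.7.

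Only the B change gives a natural coefficient.

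**4. Controls in the same table.** EASI: (4×3)×6×(0.1 + 0.3 + 0.2 + 0.4) = 72, as stated. BSA: 1/0.10 + 1/0.0333 + 1/0.05 + 1/0.025 = 100.03, which is 100 apart from the rounding of 0.0333.

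**5. Weights at maximum scores.** Severity: 9/49 = 18% with B/2, 63/103 = 61% with 7B/2. Subjective symptoms: 20/49 = 41% against 20/103 = 19%.

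**6. Effect on percent improvement (exact, no data needed).** Let b be the fractional improvement in B and r that in A/5 + C. At baseline, let w1 = (B/2)/(A/5 + B/2 + C) and w7 = (7B/2)/(A/5 + 7B/2 + C). Percent improvement is w·b + (1 − w)·r under each formula, so

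P(7B/2) − P(B/2) = (w7 − w1)(b − r).

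At maximum scores w7 − w1 is 0.428. Its upper bound is (√7 − 1)/(√7 + 1) = 0.451, reached when (B/2)/(A/5 + C) = 1/√7 = 0.378. So the formulas agree when severity and the rest improve equally, and differ by at most about 4.5 points per 10-point gap.

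**7. Illustration (assumed component scores; the documents give none).** Baseline A = 50, B = 12, C = 14 scores 30 with B/2 and 66 with 7B/2.
- Follow-up 10, 4, 2: (30 − 6)/30 = 80.0%, a responder, against (66 − 18)/66 = 72.7%, a nonresponder.
- Follow-up 10, 2, 6: (30 − 9)/30 = 70.0%, a nonresponder, against (66 − 15)/66 = 77.3%, a responder.
- Baseline 30, 9, 10: 6 + 4.5 + 10 = 20.5, outside the above-25 subset, against 6 + 31.5 + 10 = 47.5, inside it.

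**8. Who could change status.** Under SAP Section 6.3.1, patients who are censored or have a missing visit count as nonresponders whichever formula is used. In those analyses SCORAD75 and SCORAD90 status could change only for patients with uncensored data. Membership of the SCORAD<=25 subset is fixed at baseline, so this limit does not apply to it.

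**The case against.** The strongest objection is that the gap is one character, and that this table has lost characters in PDF reading. The conditions for EASI50, EASI75, EASI90, SCORAD75 and SCORAD90 all lack the minus sign before the threshold, although Table JAIN.6.9 prints it for EASI75. The SCORAD row is therefore itself damaged, and the intact EASI and BSA cells do not prove that it kept its digits. This stands as a reason for doubt. It does not settle the matter: the other losses are minus signs, not digits.

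Three further points have force.
- A programmer reading the whole row would see 103 and might notice the conflict. A separate dataset specification may also exist, since Table JAIN.6.10 names one for SF-36.
- The illustrative patients were chosen to straddle 75%. They show that status can change, not how often.
- 7B/2 follows from 103 only if the A and C terms are correct as printed.

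A reader might infer that the Week 16 SCORAD75 results, or the alpha passed on from them, are wrong. The documents do not support that. The 24-week lock was run under Version 2 and the 52-week lock under Version 3. Neither version's SCORAD line is available, and the revision history lists a Table 6.7 as changed in both Versions 3 and 4. The Version 5 line does not show which formula produced the earlier results.

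**Conclusion.** As printed, the derivation contradicts the maximum stated in its own row and in the protocol: 49 against 103. That arithmetic is exact. Whether it is a planning error or a reading loss needs the source page.

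The consequence is conditional on B/2 being both printed and programmed. In that case SCORAD75, SCORAD90 and SCORAD<=25 status could be wrong in either direction, within the limits shown above. The number of patients affected and the effect on the treatment comparison cannot be computed from the documents. EASI75 and the sample size do not depend on SCORAD.

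The final lock lists no SCORAD efficacy endpoint, but it would be wrong to conclude that the line has no remaining use. Under SAP Section 6.6, "Patient characteristics including demographics and baseline characteristics will be summarized descriptively for the" 24-week analysis and also for the final analysis in the long-term extension populations, and Section 6.6.2 includes SCORAD in that list. A descriptive baseline SCORAD summary is therefore still planned. The point is worth fixing, with medium confidence that the printed line is a real error.

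**What to change.** 1. Look at the source page of Table JAIN.6.7 and at the same line in SAP Versions 2 and 3. Where B/2 is printed, reconcile it with the stated maximum of 103. If the A and C terms are correct, the line becomes A/5 + 7B/2 + C.
2. Check the derived variable used at the 24-week and 52-week locks. The quickest test is the baseline SCORAD maximum in the 24-week patient characteristics table, which protocol Section 10.3.2.2 requires for continuous measures. Any value above 49 rules out B/2. If none exceeds 49, recompute from A, B and C.
3. Only if B/2 was programmed, rerun the SCORAD endpoints, including the SCORAD<=25 baseline subset, and the graphical procedure, and report the correction.

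The cost is a look at three versions of one line, one table value and, if needed, a one-line SAP correction. Reanalysis arises only under step 3.
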